APPENDIX 4 WOMEN OF CHILDBEARING POTENTIAL DEFINITIONS AND METHODS OF CONTRACEPTION

DEFINITIONS

Woman of Childbearing Potential (WOCBP)

A woman is considered fertile following menarche and until becoming post-menopausal unless permanently sterile. Permanent sterilization methods include hysterectomy, bilateral salpingectomy, and bilateral oophorectomy.

Women in the following categories are not considered WOCBP

- Premenarchal
- Premenopausal female with 1 of the following:
 - Documented hysterectomy
 - Documented bilateral salpingectomy
 - Documented bilateral oophorectomy

Note: Documentation can come from the site personnel's review of the participant's medical records, medical examination, or medical history interview.

- Postmenopausal female
 - A postmenopausal state is defined as 12 months of amenorrhea in a woman over age 45 years in the absence of other biological or physiological causes. In addition, females under the age of 55 years must have a serum follicle stimulating hormone (FSH) level > 40 mIU/mL to confirm menopause.

Note: Females treated with hormone replacement therapy (HRT) are likely to have artificially suppressed FSH levels and may require a washout period in order to obtain a physiologic FSH level. The duration of the washout period is a function of the type of HRT used. The duration of the washout period below are suggested guidelines and the investigators should use their judgement in checking serum FSH levels.

- 1 week minimum for vaginal hormonal products (rings, creams, gels)
- 4 week minimum for transdermal products
- 8 week minimum for oral products

Other parenteral products may require washout periods as long as 6 months. If the serum FSH level is > 40 mIU/ml at any time during the washout period, the woman can be considered postmenopausal.

End of Relevant Systemic Exposure

- End of relevant systemic exposure is the time point where the IMP or any active major metabolites has decreased to a concentration that is no longer considered to be relevant for human teratogenicity or fetotoxicity. This should be evaluated in context of safety margins from the no-observed adverse effect level (NOAEL) or the time required for 5 half-lives of the IMP to pass.

METHODS OF CONTRACEPTION

Local laws and regulations may require use of alternative and/or additional contraception methods.


Highly Effective Contraceptive Methods That Are User Dependent
 
Failure rate of < 1% per year when used consistently and correctly.^a

• Combined (estrogen- and progestogen-containing) hormonal contraception associated with inhibition of ovulation and/or implantation (This method of contraception can only be used by WOCBP participants in studies where hormonal contraception is permitted by the study protocol.)^b
– oral (birth control pills)– intravaginal (vaginal birth control suppositories, rings, creams, gels)– transdermal• Combined (estrogen-and progestogen-containing) hormonal contraception must begin at least 30 days prior to initiation of study therapy

• Progestogen-only hormonal contraception associated with inhibition of ovulation (This method of contraception can only be used by WOCBP participants in studies where hormonal contraception is permitted by the study protocol.)^b
– oral– injectable• Progestogen-only hormonal contraception must begin at least 30 days prior to initiation of study therapy

Highly Effective Methods That Are User Independent

• Implantable progestogen-only hormonal contraception associated with inhibition of ovulation and/or implantation (This method of contraception can only be used by WOCBP participants in studies where hormonal contraception is permitted by the study protocol.)^b• Intrauterine device (IUD)• Intrauterine hormone-releasing system (IUS) (This method of contraception can only be used by WOCBP participants in studies where hormonal contraception is permitted by the study protocol.)^{b,c}• Bilateral tubal occlusion

• Vasectomized partner
– For WOCBP: Having a vasectomized partner is a highly effective contraception method provided that the partner is the sole male sexual partner of the WOCBP and the absence of sperm has been confirmed. If not, an additional highly effective method of contraception should be used.


– For male participants: A vasectomy is a highly effective contraception method provided that the participant is the sole male sexual partner of the WOCBP and the absence of sperm has been confirmed. If not, an additional highly effective method of contraception should be used.• Male participants will be required to always use a latex or other synthetic condom during any sexual activity (eg, vaginal, anal, oral) with WOCBP; even if the participants have undergone a successful vasectomy or if their partner is already pregnant or breastfeeding.

• Sexual abstinence 
Sexual abstinence is considered a highly effective method only if defined as refraining from heterosexual intercourse during the entire period of risk associated with the study treatment. The reliability of sexual abstinence needs to be evaluated in relation to the duration of the study and the preferred and usual lifestyle of the participant.
 
• Continuous abstinence must begin at least 30 days prior to initiation of study therapy• It is not necessary to use any other method of contraception when complete abstinence is elected• WOCBP participants who choose complete abstinence must continue to have pregnancy tests, as specified in Section 2• Acceptable alternate methods of highly effective contraception must be discussed in the event that the WOCBP participants chooses to forego complete abstinence• Periodic abstinence (including but not limited to calendar, symptothermal, post-ovulation methods), withdrawal (coitus interruptus), spermicides only, and lactational amenorrhoea method (LAM) are not acceptable methods of contraception for this study

NOTES:
 
^a Typical use failure rates may differ from those when used consistently and correctly. Use should be consistent with local regulations regarding the use of contraceptive methods for participants participating in clinical studies.^b Hormonal contraception may be susceptible to interaction with the study treatment, which may reduce the efficacy of the contraceptive method. Hormonal contraception is permissible only when there is sufficient evidence that the IMP and other study medications will not alter hormonal exposures such that contraception would be ineffective or result in increased exposures that could be potentially hazardous. In this case, alternative methods of contraception should be utilized.^c Intrauterine hormone releasing systems are acceptable methods of contraception in the absence of definitive drug interaction studies when hormone exposures from intrauterine devices do not alter contraception effectiveness.

Less Than Highly Effective Contraceptive Methods That Are User Dependent

Failure rate of > 1% per year when used consistently and correctly.

- Male or female condom with or without spermicide. Male and female condoms cannot be used simultaneously
- Diaphragm with spermicide
- Cervical cap with spermicide
- Vaginal Sponge with spermicide
- Progestogen-only oral hormonal contraception, where inhibition of ovulation is not the primary mechanism of action (This method of contraception cannot be used by WOCBP participants in studies where hormonal contraception is prohibited.)

Unacceptable Methods of Contraception

- Periodic abstinence (calendar, symptothermal, post-ovulation methods)
- Withdrawal (coitus interruptus).
- Spermicide only
- Lactation amenorrhea method (LAM)

COLLECTION OF PREGNANCY INFORMATION

Guidance for collection of Pregnancy Information and outcome of pregnancy on the Pregnancy Surveillance Form is provided in [Section 9.2.5](#) and the Appendix for Adverse Events and Serious Adverse Events Definitions and procedures for Evaluating, Follow-up and Reporting.

**APPENDIX 5 AMERICAN COLLEGE OF RHEUMATOLOGY SUBJECT
ASSESSMENT OF DISEASE ACTIVITY VISUAL ASSESSMENT
SCALE**

Measure with a metric ruler. Line on Case Report Form is exactly 10 cm long. Scores should be recorded in millimeter format. DO NOT USE THIS APPENDIX AS SOURCE DOCUMENT OR CASE REPORT FORM.

Considering all the ways in which illness and health conditions may affect you at this time, please make a mark below to show how you are doing.

A horizontal line is drawn between two rectangular boxes. The left box contains the text "Very Well" and the right box contains the text "Very Poorly". The line is intended for a subject to mark their score.

**APPENDIX 6 AMERICAN COLLEGE OF RHEUMATOLOGY SUBJECT
ASSESSMENT OF PAIN VISUAL ASSESSMENT SCALE**

Measure with a metric ruler. Line on Case Report Form is exactly 10 cm long. Scores should be recorded in millimeter format. DO NOT USE THIS APPENDIX AS SOURCE DOCUMENT OR CASE REPORT FORM.

How much pain have you had because of your condition over the past week? Place a mark on the line below to indicate how severely your pain has been:

[figure not shown]
A horizontal line representing a 10 cm scale. On the left end, there is a vertical tick mark and a box containing the text "No Pain". On the right end, there is a vertical tick mark and a box containing the text "Pain as Bad as it Could be".

**APPENDIX 7 AMERICAN COLLEGE OF RHEUMATOLOGY PHYSICIAN
GLOBAL ASSESSMENT OF DISEASE ACTIVITY VISUAL
ASSESSMENT SCALE**

Measure with a metric ruler. Line on Case Report Form is exactly 10 cm long. Scores should be recorded in millimeter format. DO NOT USE THIS APPENDIX AS SOURCE DOCUMENT OR CASE REPORT FORM.

[figure not shown]
What is the disease activity independent of the participant's self-assessment?

[figure not shown]
Very
Good

[figure not shown]

Very
Bad

[figure not shown]
**APPENDIX 8 AMERICAN COLLEGE OF RHEUMATOLOGY SUBJECT
ASSESSMENT OF PHYSICAL FUNCTION SCALE: HEALTH
ASSESSMENT QUESTIONNAIRE (HAQ)**

[figure not shown]

[figure not shown]

[figure not shown]

APPENDIX 9 SF-36 V2.0

[figure not shown]

[figure not shown]

[figure not shown]

**APPENDIX 10 WORK PRODUCTIVITY AND ACTIVITY IMPAIRMENT
QUESTIONNAIRE-RHEUMATOID ARTHRITIS, V2.0 (WPAI-RA)**

[figure not shown]

**APPENDIX 11 FUNCTIONAL ASSESSMENT OF CHRONIC ILLNESS
THERAPY (FACIT) - FATIGUE**

APPENDIX 12 MORNING STIFFNESS DURATION

APPENDIX 13 2010 ACR-EULAR CLASSIFICATION CRITERIA FOR RHEUMATOID ARTHRITIS

The target population (Who should be tested)? Patients who:

1. have at least 1 joint with definite clinical synovitis (swelling)
2. with the synovitis not better explained by another disease

Classification criteria for RA (score-based algorithm: add score of categories A - D; a score of $\geq 6/10$ is needed for classification of a patient as having definite RA.

A. Joint involvement	
1 large joint	0
2-10 large joints	1
1-3 small joints (with or without involvement of large joints)	2
4-10 small joints (with or without involvement of large joints)	3
>10 joints (at least 1 small joint)	5
B. Serology (at least 1 test result is needed for classification)	
Negative RF and negative ACPA	0
Low-positive RF or low-positive ACPA	2
High-positive RF or high-positive ACPA	3
C. Acute-phase reactants (at least 1 test result is needed for classification)	
Normal CRP and normal ESR	0
Abnormal CRP or abnormal ESR	1
D. Duration of symptoms	
<6 weeks	0
≥ 6 weeks	1

APPENDIX 14 RA DISEASE ACTIVITY DEFINITIONS

American College of Rheumatology Core Data Set

ACR core data set component	Validated Measurement Tool
Tender joint count	Standardized 68 joint count
Swollen joint count	Standardized 66 joint count
Subject global assessment of pain	A 0-100mm visual analog scale
Subject global assessment of disease activity	A 0-100mm visual analog scale
Physician global assessment of disease activity	A 0-100mm visual analog scale
Subject assessment of physical function	Health Assessment Questionnaire (HAQ)
Acute phase reactant value	ESR (Westergren) and C-reactive protein

The ACR 20, ACR 50, or ACR 70 definition of improvement is a 20%, 50%, or 70% improvement, respectively, over baseline in tender and swollen joint counts (#1 and #2) and a 20%, 50%, or 70% improvement, respectively, in 3 of the 5 remaining core data set measures (components #3 to #7).

Disease Activity Index (DAS)28-CRP is calculated using the following formula:

$$\text{DAS28-CRP}(4) = 0.56 \cdot \sqrt{\text{TJC28}} + 0.28 \cdot \sqrt{\text{SJC28}} + 0.36 \cdot \ln(\text{CRP}+1) + 0.014 \cdot \text{GH} + 0.96$$

where t28 = number of painful joints from 28 joints, sw28 = number of swollen joints from 28 joints, CRP = c-reactive protein in mg/L, and GH = general health or patient's global assessment of disease activity on a 100 mm VAS

Simple Disease Activity Index (SDAI) is calculated using the following formula:

$$\text{TJC} + \text{SJC} + \text{PGA} + \text{MDGA} + \text{CRP}$$

Clinical Disease Activity Index (CDAI) is calculated using the following formula:

$$\text{TJC} + \text{SJC} + \text{PGA} + \text{MDGA}$$

(TJC = number of painful joints from 28 joints, SJC = number of swollen joints from 28 joints, PGA = patient global assessment on a visual analog scale 0-10 cm, MDGA = physician global assessment on a visual analog scale 0-10 cm, and CRP = c-reactive protein in mg/dL)

Boolean Remission is defined as:

Tender joint count \leq 1, Swollen joint count \leq 1, CRP \leq 1 mg/dL, patient global assessment \leq 1 (on 0 to 10 VAS scale).

**APPENDIX 15 JOINT COUNT ASSESSMENT COMPONENTS FOR DAS28
(RIGHT AND LEFT SIDE)**

Shoulder
Elbow
Wrist
MCP1
MCP2
MCP3
MCP4
MCP5
PIP1
PIP2
PIP3
PIP4
PIP5
Knee

APPENDIX 16 COUNTRY-SPECIFIC REQUIREMENTS/DIFFERENCES

Country/Location Requirement	Original Language/ Section Number	Country-specific Language or Differences
France, Germany, Czech Republic, UK	Section 8.1: Discontinuation from Study Treatment	Second paragraph following bulleted text modified to read: “In the case of pregnancy, the investigator must immediately notify the BMS Medical Monitor/designee of this event. In most cases, the study treatment will be permanently discontinued in an appropriate manner (eg, dose tapering if necessary for participant safety). Please call the BMS Medical Monitor within 24 hours of awareness of the pregnancy.”
France/Italy		Add to discontinuation criteria bullets an item for discontinuation due to product inefficacy.
France		Add to discontinuation criteria bullets an item for discontinuation due to severe infection.
Sweden	Section 9: Study Assessments and Procedures	All assessments must be performed by a qualified physician.
Japan	Table 2-1: Screening Procedural Outline (IM101863)	Add the following test at Screening: (1 to 3) β-D glucan.
	Section 6.2: Exclusion Criteria	Add the following text as criterion 3) j): “Participants who are (1 to 3) β-D glucan positive.”
	Section 9.4: Safety	Add subsection for Fungal Testing, with the following text: “The (1 to 3) β-D glucan test will be performed at the Screening visit.”
	Table 9.4.7-1: Clinical Safety Laboratory Assessments	Add (1 to 3) β-D glucan.
	Table 2-1: Screening Procedural Outline (IM101863)	Add the following test at Screening: hepatitis B surface antibody (HBsAb).
	Section 6.2: Exclusion Criteria	Replace current text for criterion 3) a) with the following text: “Hepatitis B surface antigen (HBsAg)-positive participants are excluded from the study. Participants who are HBsAg negative but positive for hepatitis B surface antibody (HBsAb) or hepatitis B core antibody (HBcAb) must also be tested for quantitative hepatitis B virus (HBV) DNA. Participants with detectable levels as specified by local guidance are excluded from the study.”

Country/Location Requirement	Original Language/ Section Number	Country-specific Language or Differences
Japan (continued)	Section 9.4.6: Viral Hepatitis Screening and Monitoring	Add the following text: “Participants who are positive for anti-HBsAb but negative for HBV DNA (as defined by the lower limit of testing sensitivity) will be allowed to be randomized. These participants will be closely monitored for clinical and laboratory signs of HBV reactivation. HBV DNA testing should be performed on a monthly basis after initiation of treatment, for 6 months, along with review of liver chemistries. After 6 months, the interval and duration of surveillance should be decided at the investigator’s discretion and in accordance with local guidelines.”
	Table 9.4.7-1: Clinical Safety Laboratory Assessments	Add HBsAb.
	Section 7.1.1.1: Abatacept Self-administration of Subcutaneous Injection	Add the following text: “Additional self-administration training for participants is allowed to be extended until Week 4. Training should be performed by unblinded study site personnel qualified in teaching patients about administration of medication in prefilled syringes. The site needs to ensure that any additional training visits do not imperil maintenance of the blind at the site (ie, shielding treatment allocation from blinded site study personnel).”
	Section 7.1.2.1: Adalimumab Self-administration of Subcutaneous Injection	Add the following text: “Additional self-administration training for participants is allowed to be extended until Week 4. Training should be performed by unblinded study site personnel qualified in teaching patients about administration of medication in prefilled syringes. The site needs to ensure that any additional training visits do not imperil maintenance of the blind at the site (ie, shielding treatment allocation from blinded site study personnel).”
	Section 9.2.9: Other Safety Considerations	Add the following text: “Malfunction of the prefilled syringes containing study treatment should be reported to the Sponsor via designated CRF. SAEs or events that could lead to an SAE that occurred as a result of the malfunction should be reported to the Sponsor within 24 hours of awareness of the event.”

Abbreviations: BMS, Bristol-Myers Squibb Company; CRF, case report form; DNA, deoxyribonucleic acid; HBcAb, hepatitis B core antibody; HBsAb, hepatitis B surface antibody; HBsAg, hepatitis B surface antigen; HBV, hepatitis B virus; SAE, serious adverse event; UK, United Kingdom.

APPENDIX 17 LABORATORY GUIDELINES: PATIENT STUDIES (REVISED AUGUST 13, 1999)

Laboratory test results, which meet these criteria, and the investigator feels is clinically relevant should be described on the Adverse Event Form. Those which are judged to be SERIOUS events require the completion of a Serious Adverse Event Form (see [Section 9.2](#)).

[NOTE: LLN = lower limit of normal; ULN = upper limit of normal.]

albumin - $<0.9 \times \text{LLN}$ or if pretreatment value is $< \text{LLN}$, $<0.75 \times$ pretreatment

alkaline phosphatase - $>2 \times \text{ULN}$; or if pretreatment $> \text{ULN}$, $3 \times$ pretreatment value

basophils (%) - $>3\%$ if $0-1\%$ pretreatment, $>3 \times$ pretreatment value if pretreatment $>1\%$

bilirubin

a) direct - $>1.5 \times \text{ULN}$, or if pretreatment above ULN, $>2 \times$ pretreatment

b) total - $>2 \times$ upper limit of normal, or if pretreatment above ULN, $>4 \times$ pretreatment value

blasts - >0

blood urea nitrogen (BUN) - $>2 \times$ pretreatment

calcium - $<0.8 \times \text{LLN}$ or $>1.2 \times \text{ULN}$; $<0.75 \times$ pretreatment if pretreatment below LLN, or $>1.25 \times$ pretreatment if pretreatment above ULN; $> \text{ULN}$ if $< \text{LLN}$ pretreatment, or $< \text{LLN}$ if $> \text{ULN}$ pretreatment

chloride - $<0.9 \times \text{LLN}$ or $>1.1 \times \text{ULN}$; or $<0.9 \times$ pretreatment if pretreatment below LLN, or $>1.1 \times$ pretreatment if pretreatment above ULN; $> \text{ULN}$ if $< \text{LLN}$ pretreatment, or $< \text{LLN}$ if $> \text{ULN}$ pretreatment

creatinine - $>1.5 \times$ pretreatment value

eosinophils (%) - $>3 \times$ pretreatment and $> 8\%$ if pretreatment normal; if pretreatment $> \text{ULN}$, $>3 \times$ pretreatment

erythrocytes - $<0.75 \times$ pretreatment value

glucose - $<0.8 \times \text{LLN}$ or $>1.5 \times \text{ULN}$; if pretreatment $< \text{LLN}$ then $<0.8 \times$ pretreatment; if pretreatment $> \text{ULN}$ then $>2 \times$ pretreatment; $< \text{LLN}$ if $> \text{ULN}$ pretreatment, or $> \text{ULN}$ if $< \text{LLN}$ pretreatment

hematocrit - $<0.75 \times$ pretreatment

hemoglobin - >3 g/dL decrease from pretreatment value

lactic dehydrogenase (LDH) - $>1.5 \times \text{ULN}$; if pretreatment value is above ULN, $>3 \times$ pretreatment value

leukocyte (WBC) count - $<0.75 \times \text{LLN}$ or $>1.25 \times \text{ULN}$; $<0.8 \times$ pretreatment if pretreatment $< \text{LLN}$ or $>1.2 \times$ pretreatment if pretreatment $> \text{ULN}$; $> \text{ULN}$ if pretreatment $< \text{LLN}$ or $< \text{LLN}$ if $> \text{ULN}$ pretreatment

lymphocytes (%) - $<0.5x$ LLN or $>2.0x$ ULN, or $<0.5x$ pretreatment if below LLN pretreatment; $>2.0x$ pretreatment if above ULN pretreatment. $>ULN$ if $<LLN$ pretreatment, or $<LLN$ if $>ULN$ pretreatment

monocytes (%) - $>2x$ ULN; $>2x$ pretreatment if pretreatment above ULN

neutrophil count (neutrophils+bands) - $<0.67x$ pretreatment if pretreatment $<1000/mm^3$; otherwise, $<1000/mm^3$.

phosphate - $<0.75x$ LLN or $>1.25x$ ULN; $<0.67x$ pretreatment value if below LLN pretreatment, or $>1.33x$ pretreatment if above ULN pretreatment; $>ULN$ if $<LLN$ pretreatment, or $<LLN$ if $>ULN$ pretreatment

platelet count - $<0.67x$ LLN or $>1.5x$ ULN; if below normal pretreatment, $<0.5x$ pretreatment value and $<100,000/mm^3$

potassium - $<0.9x$ LLN or $>1.1x$ ULN; $<0.9x$ pretreatment if pretreatment below LLN, or $>1.1x$ pretreatment if pretreatment above ULN; $>ULN$ if $<LLN$ pretreatment, or $<LLN$ if $>ULN$ pretreatment

protein, total - $<0.9x$ LLN or $>1.1x$ ULN; $<0.9x$ pretreatment if below LLN pretreatment, or $>1.1x$ ULN if above ULN pretreatment; $>ULN$ if $<LLN$ pretreatment, or $<LLN$ if $>ULN$ pretreatment

SGOT and SGPT (ASAT and ALAT) - $>3x$ upper limit of normal; if pretreatment above ULN, $>4x$ pretreatment value

sodium - $<0.95x$ LLN or $>1.05x$ ULN; $<0.95x$ pretreatment if below LLN pretreatment, $>1.05x$ pretreatment if above ULN pretreatment; $>ULN$ if $<LLN$ pretreatment, or $<LLN$ if $>ULN$ pretreatment

uric acid - $>1.5x$ ULN; if pretreatment above ULN, $>2x$ pretreatment value

urinalysis

- a) urinary protein - >1 gram/24 hours and $2x$ pretreatment value
- b) urinary RBC - $>5/HPF$ or, $>4x$ pretreatment if pretreatment value $5/HPF$
- c) urinary WBC - $>5/HPF$ or, $>4x$ pretreatment if $5/HPF$ pretreatment
- d) creatinine clearance (glomerular filtration rate) - $<0.67x$ pretreatment value
- e) urine dipstick measurements: Protein, blood, sugar, and acetone- 2+, or if 1+pretreatment, $2x$ pretreatment. Do not evaluate protein if quantitative protein determination done

stool hemocult - positive if negative pretreatment

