10.3.2 Safety Analyses

The proportion (%) of participants with AEs, deaths, SAEs, AEs of special interest, and AEs leading to discontinuation and of participants with laboratory marked abnormalities will be provided by treatment group. Summaries for the SBTP will include events from the start of study treatment up to start of the OLTP for participants continuing in the OLTP or up to last dosing date +56 days for participants discontinuing during the SBTP using the as-treated analysis population. AEs of special interest are infections, malignancies, autoimmune disorders, and injection-site reactions. Summaries for the cumulative abatacept period will include safety events with onset on or after the first day of abatacept treatment in the study up to 56 days after the last abatacept treatment in the study using the cumulative abatacept population.

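### In Appendix 17, the total-protein limit for participants who start above ULN repeats the general 1.1 × ULN limit, so it makes no baseline adjustment

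*Combined protocol and SAP*

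**What the plan says.** The total-protein entry in Appendix 17 opens with general limits, "protein, total - $<0.9x$ LLN or $>1.1x$ ULN". It then sets limits for participants who are already abnormal before treatment. On the low side the limit is "<0.9x$ pretreatment if below LLN pretreatment". On the high side it is "or $>1.1x$ ULN if above ULN pretreatment".

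The chloride and potassium entries have the same general limits, and both say "or $>1.1x$ pretreatment if pretreatment above ULN" for a participant who starts high. Sodium has ">1.05x$ pretreatment if above ULN pretreatment" and phosphate has "or $>1.33x$ pretreatment if above ULN pretreatment".

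Total protein is in the chemistry panel (Table 9.4.7-1), and Section 9.4.7 refers to Appendix 17 for laboratory guidelines. The opening of Appendix 17 asks for an Adverse Event Form entry when a result meets a criterion and the investigator also considers it clinically relevant. Separately, Section 10.3.2 states that the proportion of "participants with laboratory marked abnormalities will be provided by treatment group". It does not name the limits that define those abnormalities.

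**The concern.** A clause written for participants with a high pretreatment value ought to treat them differently from everyone else. This one does not. The limit it sets is the one that already applies to a participant with a normal baseline, so someone who starts well above ULN can meet the criterion without any change on treatment.

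What is at stake is a clean separation of baseline status from on-treatment change for this analyte. Chemistry is scheduled at 6 post-baseline visits through Week 24 (Table 2-2) and at 10 more through Week 104 (Table 2-3), so one stable high value could meet the criterion at up to 6 + 10 = 16 visits. At the site, each such result is put forward for an adverse event decision. In a programmed table, if one uses these limits, no clinical judgment would filter it.

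**Working it through.** **Comparison within Appendix 17.** High-side limits only:

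| Entry | General limit | Limit if pretreatment is above ULN |
|---|---|---|
| Chloride | 1.1 × ULN | 1.1 × pretreatment |
| Potassium | 1.1 × ULN | 1.1 × pretreatment |
| Sodium | 1.05 × ULN | 1.05 × pretreatment |
| Calcium | 1.2 × ULN | 1.25 × pretreatment |
| Phosphate | 1.25 × ULN | 1.33 × pretreatment |
| **Total protein** | **1.1 × ULN** | **1.1 × ULN** |

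The other entries with an explicit high-side limit for a pretreatment value above ULN are alkaline phosphatase, direct and total bilirubin, eosinophils, glucose, LDH, leukocytes, lymphocytes, monocytes, SGOT/SGPT and uric acid. All use a multiple of the pretreatment value. Total protein is the only exception.

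**How the clauses must be read.** Let B be the pretreatment value and V the on-study value, both in multiples of ULN. For potassium with B above 1, the baseline-specific limit 1.1 × B is higher than the general limit of 1.1. If both limits applied together, the baseline-specific one could never matter. It therefore has to replace the general limit for those participants, and I read total protein the same way.

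**Size of the effect.** The printed total-protein rule flags V > 1.1. The change from baseline at which this happens is 1.1/B − 1. A rule of V > 1.1 × B requires a rise of more than 10% at every B above 1. The values of B are illustrative, because the documents give no distribution of total protein.

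| B (× ULN) | 1.1/B − 1 | Printed rule flags |
|---|---|---|
| 1.05 | 1.1/1.05 − 1 = +4.8% | a rise of more than 4.8% |
| 1.08 | 1.1/1.08 − 1 = +1.9% | a rise of more than 1.9% |
| 1.10 | 0% | any rise |
| 1.12 | 1.1/1.12 − 1 = −1.8% | no change, or a fall of less than 1.8% |
| 1.15 | 1.1/1.15 − 1 = −4.3% | no change, or a fall of less than 4.3% |
| 1.20 | 1.1/1.20 − 1 = −8.3% | no change, or a fall of less than 8.3% |

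**Individual cases, printed rule against a pretreatment-based rule:**

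- 1.15 unchanged: flagged as printed, not flagged under the pretreatment rule.
- 1.20 falling to 1.12 (−6.7%): flagged as printed, not flagged under the pretreatment rule.
- 1.08 rising to 1.11 (+2.8%): flagged as printed, not flagged under the pretreatment rule.
- 1.05 unchanged: flagged under neither.
- 1.20 rising to 1.33 (+10.8%): flagged under both.

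**The case against.** Four points can be made for leaving the text alone.

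- **Clinical judgment filters the result.** Appendix 17 requires the investigator to find the result clinically relevant. Appendix 3 defines an adverse event as something new or a worsening. Section 9.2.6 captures results that are clinically significant, meet the serious definition, or lead to interruption, discontinuation or corrective therapy. An unchanged total protein would not ordinarily pass. This stands, and it limits the consequence at the site.
- **The link to the safety summary is not written down.** Section 10.3.2 does not cite Appendix 17. Appendix 17 presents itself as a guide to adverse event reporting, and the documents reviewed contain no SAP text that sets the limits. This also stands, so any effect on that summary is conditional.
- **The appendix does not always adjust for a high baseline.** The platelet entry flags values above 1.5 × ULN with no clause for a high start. That is true, but the platelet entry leaves the clause out. Total protein includes one that has no effect, which looks like a drafting slip rather than a choice.
- **The list is generic.** It carries a 1999 revision date and includes tests outside Table 9.4.7-1, such as LDH and uric acid. But total protein is in that table, and Section 9.4.7 points to this appendix.

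A reader might also infer that any participant above ULN at baseline is flagged without change. That is not so: from a baseline between 1.0 and 1.1 × ULN a rise is still needed. Nor is +10% the general standard for the parallel entries. It holds for chloride and potassium, while sodium is +5%, calcium +25% and phosphate +33%.

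**Conclusion.** The clause is wrong as written, and its impact is low. It duplicates the general limit and conflicts with the low side of its own line, with chloride and potassium, and with every other explicit high-baseline limit in the appendix. Above 1.1 × ULN at baseline, an unchanged or slightly lower value meets the criterion. Between 1.0 and 1.1 × ULN, a rise of less than 10% is enough.

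The documents do not support the stronger inference that adverse event counts or the marked-abnormality summary will be inflated. The first depends on investigator judgment, and the second on a link that Section 10.3.2 does not make. The rule is the same in both arms, concerns one analyte, and touches no efficacy endpoint. The share of participants who start above ULN is not given, so the number affected cannot be estimated and may be nil. The conclusion rests on reading the baseline-specific limits as replacing the general ones, the only reading under which the chloride and potassium clauses have any effect.

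**What to change.** Reconcile the high-baseline clause for total protein with the low side of its own line and with the chloride and potassium entries, so that it refers to the pretreatment value instead of ULN. With a limit of 1.1 × pretreatment, no unchanged or falling value can be flagged high in a participant who starts above ULN.

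Confirm which limits define the marked abnormalities in Section 10.3.2. If they are those of Appendix 17, program the summary from the corrected limit.

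The cost is one word in the appendix and, if the link is confirmed, one programming limit. No visit, sample or efficacy analysis changes.
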